7.2 Adverse Event Characteristics

- **CTCAE term (AE description) and grade:** The descriptions and grading scales found in the revised NCI Common Terminology Criteria for Adverse Events (CTCAE) version 4.0 will be utilized for AE reporting. All appropriate treatment areas should have access to a copy of the CTCAE version 4.0. A copy of the CTCAE version 4.0 can be downloaded from the CTEP web site http://ctep.cancer.gov/protocolDevelopment/electronic_applications/ctc.htm.
- **Attribution** of the AE:
 - Definite – The AE is *clearly related* to the study treatment.
 - Probable – The AE is *likely related* to the study treatment.
 - Possible – The AE *may be related* to the study treatment.
 - Unlikely – The AE is *doubtfully related* to the study treatment.
 - Unrelated – The AE is *clearly NOT related* to the study treatment.

7.3 Expedited Adverse Event Reporting

7.3.1 Investigators **must** report to the Overall PI any serious adverse event (SAE) that occurs after the initial dose of study treatment, during treatment, or within 30 days of the last dose of treatment on the local institutional SAE form.

7.4 Expedited Reporting to the Food and Drug Administration (FDA)

The Overall PI, as study sponsor, will be responsible for all communications with the FDA. The Overall PI will report to the FDA, regardless of the site of occurrence, any serious adverse event that meets the FDA's criteria for expedited reporting following the reporting requirements and timelines set by the FDA.

7.5 Expedited Reporting to Hospital Risk Management

Participating investigators will report to their local Risk Management office any participant safety reports or sentinel events that require reporting according to institutional policy.

7.6 Routine Adverse Event Reporting

All Adverse Events **must** be reported in routine study data submissions to the Overall PI on the toxicity case report forms. **AEs reported through expedited processes (e.g., reported to the IRB, FDA, etc.) must also be reported in routine study data submissions.**

7.7 Adverse Event Reporting

CONFIDENTIAL

This document is confidential. Do not disclose or use except as authorized.

7.7.1 In the event of an unanticipated problem or life-threatening complications treating investigators must immediately notify the PI

7.7.2 Investigators **must** report to the PI any adverse event (AE) that occurs after the initial dose of study treatment, during treatment, or within 30 days of the last dose of treatment on the local institutional SAE form.

7.7.3 Adverse Event Reporting Guidelines

All participating sites will report AEs to the Sponsor-Investigator per DF/HCC requirements, and the IRB of record for each site as applicable per IRB policies. The table below indicates which events must be reported to the DF/HCC Sponsor-Investigator.

Attribution	DF/HCC Reportable Adverse Events(AEs)				
	Gr. 2 & 3 AE Expected	Gr. 2 & 3 AE Unexpected	Gr. 4 AE Expected	Gr. 4 AE Unexpected	Gr. 5 AE Expected or Unexpected
Unrelated Unlikely	Not required	Not required	5 calendar days [#]	5 calendar days	24 hours*
Possible Probable Definite	Not required	5 calendar days	5 calendar days [#]	5 calendar days	24 hours*

If listed in protocol as expected and not requiring expedited reporting, event does not need to be reported.

* For participants enrolled and actively participating in the study **or** for AEs occurring within 30 days of the last intervention, events must be reported within 1 business day of learning of the event.

7.8 Immediate Reporting of Adverse Events and Events of Clinical Interest to Merck

7.8.1 Serious Adverse Events

A serious adverse event is any adverse event occurring at any dose or during any use of Merck's product that:

- Results in death;
- Is life threatening;
- Results in persistent or significant disability/incapacity;
- Results in or prolongs an existing inpatient hospitalization;
- Is a congenital anomaly/birth defect;
- Is a new cancer (that is not a condition of the study);
- Is associated with an overdose;
- Is another important medical event

7.8.2 Reporting Requirements for Participating Investigators

CONFIDENTIAL

This document is confidential. Do not disclose or use except as authorized.

Each participating investigator is required to abide by the reporting requirements set by the DF/HCC. The study must be conducted in compliance with FDA regulations, local safety reporting requirements, and reporting requirements of the principal investigator.

It is the responsibility of each participating investigator to report adverse events within 48 hours to the Overall PI, [name], MD, MPH (at the contact given below), or representative personnel; and submit to DFCI IRB within 10 working days.

[name], MPH
[contact]
[contact]

7.8.3 Reporting Requirements for DFCI IRB

Investigators **must** report to the Overall PI any serious adverse event (SAE) that occurs after the initial dose of study treatment, during treatment, or within 30 days of the last dose of treatment on the local institutional SAE form.

7.8.4 Reporting Requirements for Merck

Any serious adverse event, or follow up to a serious adverse event, including death due to any cause other than progression of the cancer under study that occurs to any subject from the time the consent is signed through 30 days following cessation of treatment, or the initiation of new anti-cancer therapy, whichever is earlier, whether or not related to Merck product, must be reported within 2 working days to Merck Global Safety.

Non-serious Events of Clinical Interest will be forwarded to Merck Global Safety and will be handled in the same manner as SAEs.

Additionally, any serious adverse event, considered by an investigator who is a qualified physician to be related to Merck product that is brought to the attention of the investigator at any time outside of the time period specified in the previous paragraph also must be reported immediately to Merck.

SAE reports and any other relevant safety information are to be forwarded to the Merck Global Safety [contact]

A copy of all 15 Day Reports and Annual Progress Reports is submitted as required by FDA, European Union (EU), Pharmaceutical and Medical Devices agency (PMDA) or other local regulators. Investigators will cross reference this submission according to local regulations to the Merck Investigational Compound Number (IND, CSA, etc.) at the time of submission. Additionally, investigators will submit a copy of these reports to Merck & Co., Inc. (Attn: Worldwide Product Safety; [contact]) at the time of submission to FDA.

All subjects with serious adverse events must be followed up for outcome.

CONFIDENTIAL

This document is confidential. Do not disclose or use except as authorized.

7.8.5 Events of Clinical Interest (ECIs)

Selected non-serious and serious adverse events are also known as Events of Clinical Interest (ECI) and must be recorded as such on the Adverse Event case report forms/worksheets and reported within 24 hours to the Sponsor and within 2 working days to Merck Global Safety. (Attn: Worldwide Product Safety; [contact]). Events of clinical interest for this trial include:

1. an overdose of Merck product, as defined in Section 7.7.3 - Definition of an Overdose for This Protocol and Reporting of Overdose to Merck, that is not associated with clinical symptoms or abnormal laboratory results.
2. an elevated AST or ALT lab value that is greater than or equal to 3X the upper limit of normal and an elevated total bilirubin lab value that is greater than or equal to 2X the upper limit of normal and, at the same time, an alkaline phosphatase lab value that is less than 2X the upper limit of normal, as determined by way of protocol-specified laboratory testing or unscheduled laboratory testing.*

***Note:** These criteria are based upon available regulatory guidance documents. The purpose of the criteria is to specify a threshold of abnormal hepatic tests that may require an additional evaluation for an underlying etiology. The trial site guidance for assessment and follow up of these criteria can be found in the Investigator Trial File Binder (or equivalent).

Additional adverse events:

A full document entitled “Event of Clinical Interest Guidance Document” (previously entitled, “Event of Clinical Interest and Immune-Related Adverse Event Guidance Document”), which provides guidance regarding identification, evaluation and management of ECIs and irAEs, is in the possession of the PI and can be accessed upon request.

ECIs (both non-serious and serious adverse events) identified from the date of first dose through 90 days following cessation of treatment, or 30 days after the initiation of a new anticancer therapy, whichever is earlier, need to be reported within 24 hours to the Sponsor and within 2 working days to Merck Global Safety. (Attn: Worldwide Product Safety; [contact]), regardless of attribution to study treatment, consistent with standard SAE reporting guidelines.

Subjects should be assessed for possible ECIs prior to each dose. Lab results should be evaluated and subjects should be asked for signs and symptoms suggestive of an immune-related event. Subjects who develop an ECI thought to be immune-related should have additional testing to rule out other etiologic causes. If lab results or symptoms indicate a possible immune-related ECI, then additional testing should be performed to rule out other etiologic causes. If no other cause is found, then it is assumed to be immune-related.

7.8.6 Definition of an Overdose of pembrolizumab for This Protocol and Reporting of Overdose to Merck

CONFIDENTIAL

This document is confidential. Do not disclose or use except as authorized.

For purposes of this trial, an overdose of pembrolizumab will be defined as any dose of 1,000 mg or greater. No specific information is available on the treatment of overdose of pembrolizumab. Appropriate supportive treatment should be provided if clinically indicated. In the event of overdose, the subject should be observed closely for signs of toxicity. Appropriate supportive treatment should be provided if clinically indicated.

If an adverse event(s) is associated with (“results from”) the overdose of a Merck product, the adverse event(s) is reported as a serious adverse event, even if no other seriousness criteria are met.

If a dose of Merck’s product meeting the protocol definition of overdose is taken without any associated clinical symptoms or abnormal laboratory results, the overdose is reported as a non-serious Event of Clinical Interest (ECI), using the terminology “accidental or intentional overdose without adverse effect.”

All reports of overdose with and without an adverse event must be reported within 24 hours to the Sponsor and within 2 working days hours to Merck Global Safety. (Attn: Worldwide Product Safety; [contact])

7.8.7 Reporting of Pregnancy and Lactation to Merck

Although pregnancy and lactation are not considered adverse events, it is the responsibility of investigators or their designees to report any pregnancy or lactation in a subject (spontaneously reported to them), including the pregnancy of a male subject's female partner that occurs during the trial or within 120 days of completing the trial completing the trial, or 30 days following cessation of treatment if the subject initiates new anticancer therapy, whichever is earlier. All subjects and female partners of male subjects who become pregnant must be followed to the completion/termination of the pregnancy. Pregnancy outcomes of spontaneous abortion, missed abortion, benign hydatidiform mole, blighted ovum, fetal death, intrauterine death, miscarriage and stillbirth must be reported as serious events (Important Medical Events). If the pregnancy continues to term, the outcome (health of infant) must also be reported.

Such events must be reported 2 working days to Merck Global Safety. (Attn: Worldwide Product Safety; [contact])

8. PHARMACEUTICAL INFORMATION

A list of the adverse events and potential risks associated with the investigational and other agents administered in this study can be found in Section 7.1.

8.1 Pembrolizumab

Please refer to the Investigator’s Brochure for detailed agent information, and to the FDA label for additional information.

CONFIDENTIAL

This document is confidential. Do not disclose or use except as authorized.

8.1.1 **Description**

Pembrolizumab is a humanized monoclonal antibody of the IgG4/kappa isotype. Other name: MK-3475, Keytruda. Pembrolizumab blocks negative immune regulatory signaling by binding to the PD-1 receptor, inhibiting the interaction between PD-1 and its ligands.

The molecular weight of Pembrolizumab is 148.9-149.5 KDa.

8.1.2 **Form**

Clinical supplies will be manufactured and provided by Merck as summarized in Table 7.

Table 7: Product Description

Product Name & Potency	Dosage Form
Pembrolizumab 100 mg/ 4mL	Solution for Injection

8.1.3 **Storage and Stability**

Store intact vials between 2°C-8°C (36°F-46°F). Do not freeze. Protect from light by storing in the original box.

Stability testing of the intact vials is ongoing.

Administer prepared solutions immediately after preparation. If not administered immediately, prepared solutions may be stored refrigerated for up to 20 hours. PEMBROLIZUMAB solutions may be stored at room temperature for a cumulative time of up to 4 hours. This includes room temperature storage of liquid drug product solution in vials, room temperature storage of infusion solution in the IV bag, and the duration of infusion.

8.1.4 **Compatibility**

Compatible IV bag materials: PVC plasticized with DEHP, non-PVC (polyolefin), EVA, or PE lined polyolefin.

8.1.5 **Handling**

Qualified personnel, familiar with procedures that minimize undue exposure to themselves and the environment, should undertake the preparation, handling, and safe disposal of the chemotherapeutic agent in a self-contained and protective environment.

8.1.6 **Availability**

Pembrolizumab is an investigational agent and will be supplied free of charge from Merck.

CONFIDENTIAL

This document is confidential. Do not disclose or use except as authorized.

8.1.7 **Preparation**

Pembrolizumab solution for infusion must be diluted prior to administration. Allow the required number of vials to equilibrate to room temperature. Do not shake the vials. Do not use if opaque or extraneous particulate matter other than translucent to white proteinaceous particles is observed. Do not use if discolored. To prepare the infusion solution add the dose volume of Pembrolizumab to an infusion bag containing 0.9% Sodium Chloride Injection, USP or 5% Dextrose Injection, USP. Gently invert the bag 10-15 times to mix the solution. The final concentration must be between **1 mg/mL to 10 mg/mL**.

8.1.8 **Administration**

Route of administration: IV infusion only. Do not administer as an IV push or bolus injection.

Method of administration: Infuse over approximately 30 minutes (range: 20-75 minutes) using an infusion set containing a low-protein binding 0.2 to 5 μm in-line filter made of polyethersulfone or polysulfone. Infusion rate should not exceed 6.7 mL/min. A central line is not required however if a subject has a central venous catheter in place, it is recommended that it be used for the infusion. Do not co-administer drugs through the same infusion line. Following the infusion, flush the IV line with normal saline.

8.1.9 **Ordering**

Pembrolizumab will be obtained directly from Merck Pharmaceuticals.

8.1.10 **Accountability**

The investigator, or a responsible party designated by the investigator, should maintain a careful record of the inventory and disposition of the agent using the NCI Drug Accountability Record Form (DARF) or another comparable drug accountability form. (See the NCI Investigator's Handbook for Procedures for Drug Accountability and Storage.)

8.1.11 **Destruction and Return**

At the end of the study, unused supplies of pembrolizumab should be destroyed according to institutional policies. Destruction will be documented in the Drug Accountability Record Form.

9. BIOMARKER, CORRELATIVE, AND SPECIAL STUDIES

Background information on the pre-clinical and clinical rationale for these investigations is discussed in Section 2.

Correlative studies to be performed on tissue collected are described in section 9.1.

CONFIDENTIAL

This document is confidential. Do not disclose or use except as authorized.

In all patients, either archival tissue or baseline biopsy is required for enrollment. Even if archival tissue is available, in all patients in whom a tumor deposit is safely accessible, a baseline tumor biopsy is suggested. In terms of archival tissue, we will attempt to obtain archival tissue taken from biopsies performed prior to the start of any immune therapy as well as after progression on immune therapy. We plan to use archival / baseline biopsy tissue to perform a number of immune profiling assays, detailed below. On baseline tumor biopsies, we will perform characterization based on immunohistochemistry for PD-L1 and other immune markers, and mRNA expression. Additionally, we plan future DNA analysis, and associated testing including whole exome sequencing.

An optional sequential biopsy will also be performed after cycle 2, within 14 days prior to cycle 3 of therapy. We will perform immunohistochemical and mRNA analyses on these specimens to determine the impact of combined radiation PD-1 blockade on immunologic parameters.

Serial blood draws for correlative science should be obtained at baseline, at week 4 or cycle 2, then again at week 7 or cycle 3, and optionally at later cycles. On each blood draw, we will perform flow cytometry and / or CyTOF analyses to characterize protein expression of immune mediators, detailed below, and additional blood will be banked for future testing, including Luminex cytokine profiling.

Sequential imaging is included in this trial for staging purposes and to monitor subsequent response to treatment. De-identified images will also be used for correlative imaging studies evaluating the potential of irradiated lesions to stimulate distant abscopal responses based on hypothetical T-cell trafficking as described above and by Poleszczuk et al. [61].

When adequate tissue is available, we will also assess PD-L1 expression via QualTek external services using the 22C3 antibody. Tumor will be considered positive if >5% (PD-L1) or >10% (PD-L2) of the tumor cell population demonstrates unequivocal staining. PD-1 positivity will be defined as >3% positive cells/high power field. All IHC stained slides will be evaluated and scored by a pathologist. A subset of slides will be reviewed by a second pathologist to ensure concordance of interpretation.

9.1 Characterizing the immunologic microenvironment of SCCHN

9.1.1 Hypotheses

- This study will enroll patients who have previously failed to benefit or progressed on PD-1 pathway directed therapy. We will attempt to identify mechanisms of resistance to PD-1 pathway inhibitors by interrogating the tumor microenvironment. Specifically, we hypothesize that resistant tumors will:
 - Demonstrate low levels of PD-L1 expression compared to an unselected population of historical controls or previously reported populations of responding patients
 - Have relatively few numbers of tumor infiltrating infiltrates compared to an unselected population of historical controls or previously reported populations of responding patients

CONFIDENTIAL

This document is confidential. Do not disclose or use except as authorized.

- This study will also obtain sequential biopsies before and after radiation to evaluate whether targeted radiation can change the local tumor microenvironment, specifically, whether:
 - Radiation increases PD-L1 expression on tumor cells
 - Radiation increases T-cell infiltration into tumor deposits

9.1.2 Collection, handling and transportation of biopsy specimens

Biopsies should not be performed on Friday afternoons, as there may not be time for processing of the fresh tissue.

If feasible, the protocol will require 2 cores, additional cores (up to 7) will be obtained using an optional consent form.

The order of specimen collection should be:

- First core: 10% neutral buffered formalin
- Second core: Sterile DMEM or RNAlater

Optional cores are alternated between formalin and sterile DMEM/ RNAlater.

After being obtained, processing of the cores is as follows:

- All samples should be de-identified
 - Formalin specimens will be processed into Formalin-fixed paraffin embedded block(s) and or unstained/unbaked slides (15-20), stored at room temperature, as per institutional procedure.
 - Tissue stored in DMEM or RNAlater will be stored at -70 to -80 degrees C.

The study coordinator should be notified before a biopsy specimen is taken / sent to arrange for transfer to the Center for Immuno-Oncology and Core Pathology Laboratories at Dana-Farber Cancer Institute / Brigham and Women's Hospital and to provide most up to date contact and shipping information.

As general guidance , samples should be transported or shipped to:

(DMEM/RNAlater samples):

Center for Immuno-Oncology
Dana-Farber Cancer Institute
[name]
[name]
[contact]

Formalin samples:

Brigham & Women's Hospital
[name]
[name]
[name]

CONFIDENTIAL

This document is confidential. Do not disclose or use except as authorized.

Note: DMEM/RNALater samples should be transported / shipped on dry ice.

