9.5 Site Performing Correlative Studies

Pathological studies will be conducted by the Center for Immune Oncology at the DFCI. QualTek, Nanostring, and other external fee-for-service services may also be performed on deidentified specimens and used for PD-L1, RNA and other analyses as specified above. Flow cytometry assessment of both tissue and blood will be performed by the Center for Immune Oncology at the DFCI. Other analyses on tumor tissue and collected samples will be performed in the laboratory of [name], a surgical oncologist at the Dana Farber Cancer Institute, who has performed similar analyses on other human tissues. Deidentified data related to correlative analyses will be shared with NYU Langone Health as a collaborator to assist with data analysis and manuscript writeup, with an agreement in place prior to sending any deidentified data.

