APPENDIX G: TIL isolation from solid tumors

1. Prepare an enzyme solution of collagenase, hyaluronidase and deoxyribonuclease in advance:
2. Dissolve collagenase (collagenase type I, cat#17100-017, Invitrogen) in DMEM at a concentration of 1 mg/ml
3. Add hyaluronidase (hyaluronidase type V, cat#H6254, Sigma-Aldrich) to a final concentration of 1mg/ml (1,500 units/ml) and deoxyribonuclease (deoxyribonuclease I, type IV, cat#5025, Sigma-Aldrich) to a final concentration of 50 micrograms/ml (100 units/ml)
4. Filter the solution with a 10 ml sterile syringe, a sterile 23G needle, and a sterile 0.2 μ m filter.
5. Record the date and time of the start of TIL isolation.*
6. Dissect patient tumor sample into pieces as small as possible with sterile scissor or scalpel. **Note:** Mincing of tumor may be facilitated by lining up two scalpels in parallel.
7. Submerge the pieces of tumor in 5 - 10 ml prepared enzyme solution in a 50 ml conical tube.
8. Enzymatically digest tumor pieces in 37°C waterbath for one to two hours; every 15 min., vigorously shake the tube.
9. Put a sterile cell strainer (100 μ m, 352360, BD Falcon) on a 50 ml conical tube, and pass the digested tumor solution through the strainer; the flowthrough will be collected in the 50 ml conical tube. Rinse the strainer and undigested tumor once with PBS.
10. Add 2-5 ml complete DMEM medium (with 10% FBS + 50 μ g/ml gentamycin) into flowthrough to stop digestion.
11. Spin the tube at 1500 rpm for 5 min in a centrifuge at room temperature.
12. In the meantime, put undigested tumor tissue into a sterile 50 ml conical tube, and add 5-10 ml enzyme solution and continue with digestion from step 4.
13. Repeat step 3 to step 8, based on tissue digestion

NOTE: For samples with lot of red blood cells and/or undigested debris that has passed through the cell strainer, the following is recommended before proceeding to step 11:

- A. Resuspend the cell pellet in 10 ml complete DMEM medium
- B. Add 10 ml Ficoll Paque Plus (Cat# 17-1440-03; GE Healthcare) in a 50 ml conical tube.
- C. Slowly and gently layer the digested tumor suspension onto the Ficoll Paque Plus.
- D. Centrifuge the tube at room temperature at 1500 - 2000 rpm (1000 g) with slow acceleration and deceleration for 20 - 30 min.

E. Pipette off the interface between complete DMEM and the Ficoll Paque Plus (lower part), and transfer the layer into a 50 ml conical tube. The bottom pellet will be composed of red blood cells and undigested debris.

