F. Add 2 - 3X bed volume of PBS to dilute Ficoll.

G. Spin the tube at 1500 rpm for 5 min in a centrifuge at room temperature.

H. Aspirate supernatant and proceed to step 11.

1. Resuspend cell pellets in complete DMEM medium plus gentamycin 50ug/ml and combine cells-TIL into one sterile 50 ml conical tube.
2. Centrifuge at 1500 rpm for 5 min in a centrifuge at room temperature.
3. Aspirate off the supernatant and remove a small aliquot to record the cell count and viability, then place the tube on ice.
4. For each timepoint, collect the following parameters:
 - a. Cell viability (%) before freezing*
 - b. Total yield of TIL (x 10⁶ cells/mL/vial) isolated prior to freezing*
5. Resuspend the cell suspension in pre-chilled PBMC freezing media (CTL-cryoABS kit, CTL cellular Technology)
 - c. Transfer 1 ml aliquots of the cell suspension to a cryovial labeled with the **supplied Quintiles labels**. A minimum of one (1) cryovial should be obtained with a minimum concentration of cells at 1x10⁶ cells/mL/vial.
 - d. For each cryovial prepared, please record the total # of cells in the cryovial*. If there are more than 2x10⁶ cells, then aliquot cells into as many cryovials as possible at a concentration of 1x10⁶ cells/ml/vial.
6. Store in 1 ml aliquots in cryovials at -80⁰C in a slow freeze container. Leave undisturbed overnight or for a **minimum of 12 hrs and a maximum of 24 hrs**.
7. Transfer into liquid nitrogen for long-term storage. Record the time, date, and location that the samples* were placed in liquid nitrogen storage.
8. At the sponsor's request, samples should be batch shipped at the end of study. Please, follow the shipping instructions provided. Samples will be shipped on liquid nitrogen.

CONFIDENTIAL

This document is confidential. Do not disclose or use except as authorized.

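### As written, no handling route brings an unfrozen biopsy core to the TIL isolation in Appendix G, so the exploratory flow cytometry on tissue would probably fail

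*Combined protocol and SAP*

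**What the plan says.** Section 9.1.2 sends the first core to formalin. For the next it specifies "Second core: Sterile DMEM or RNAlater", with no rule for choosing between the two media. Beyond the two cores required when feasible, "Optional cores are alternated between formalin and sterile DMEM/ RNAlater". Formalin cores become blocks or slides. For the rest the processing instruction is "Tissue stored in DMEM or RNAlater will be stored at -70 to -80 degrees C", and the shipping note reads "Note: DMEM/RNALater samples should be transported / shipped on dry ice". The same section opens with a scheduling rule: "Biopsies should not be performed on Friday afternoons, as there may not be time for processing of the fresh tissue".

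Appendix G describes TIL isolation. The tumor is minced, and the operator is told to "Enzymatically digest tumor pieces in 37°C waterbath for one to two hours". The parameters to be recorded include "Cell viability (%) before freezing". Only then is the cell suspension placed in a dedicated freezing medium and cooled in a slow-freeze container.

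Appendix H (flow cytometry) starts from a thawed vial of cells and cultures them overnight. Section 9.5 states: "Flow cytometry assessment of both tissue and blood will be performed by the Center for Immune Oncology at the DFCI". Section 9.1.3 is weaker and lists flow cytometry among the things for which available tissue may be used.

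**The concern.** The collection section and the assay appendices do not connect. Appendix G presupposes tissue that can still yield live cells, and puts freezing at the end, after isolation. Section 9.1.2 freezes the tissue itself at the start. A coordinator who follows section 9.1.2 to the letter would deliver frozen cores to the laboratory that section 9.5 names for tissue flow cytometry.

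At stake are the flow-based tissue readouts: TIL yield and viability under Appendix G, and the immune populations that sections 9.1.3 and 9.5 would measure on tissue. The error could not be repaired afterwards, because a core frozen this way cannot later be made suitable for digestion. Cores are also scarce. Biopsies are suggested or optional (sections 5.3.1 and 9), and section 13.2 caps enrolment at 26.

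**Working it through.** No arithmetic applies: the plan gives no figure on this point. The check sets the handling texts side by side and looks for a route from biopsy to live cells.

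1. **Section 9.1.2, formalin cores.** Fixed and embedded. Suitable for IHC, not for digestion to live cells.

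2. **Section 9.1.2, DMEM or RNAlater cores.** Stored at -70 to -80 C and moved on dry ice. Both media share one storage line and one dry-ice note. No cryoprotectant, unfrozen branch or time limit to the laboratory is given.

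3. **Appendix C.** Cores are placed in OCT, frozen on dry ice and kept at -80 C. The paragraph headed Fresh Tissue Shipping Procedures in fact ships frozen specimens on dry ice. This is a further handling text, and it does not lead to live cells either.

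4. **Appendix G.** Starts from a patient tumor sample and has no thaw step. The sequence is mince, digest at 37 C, count and record viability, then freeze the isolated cells in freezing media.

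5. **Appendix H.** Thaws a vial of cells and cultures them, with activation beads added to one flask. It needs viable cells, but they may have been cryopreserved. The frozen suspension from Appendix G would serve; a frozen core would not.

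Items 1 to 3 are the written fates of a core, and none arrives at item 4 before freezing.

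**Would a frozen core still work?** The documents do not say. That tissue frozen without cryoprotectant, or placed in RNAlater, gives no usable live cells is general laboratory knowledge. The indirect support is that, wherever the plan freezes cells to keep them, it protects them: freezing media and slow cooling in Appendix G, and 15% DMSO in serum with a controlled-cooling container in Appendix I.

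**What depends on the missing route?**

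| Use of biopsy tissue | Where stated | Supported by the written handling? |
|---|---|---|
| IHC for PD-L1 and immune markers | 9, Appendices D and F | Yes, formalin cores |
| mRNA analysis | 9, 9.1.3 | Yes, frozen cores |
| Exome and T-cell receptor sequencing | 9.1.3 | Yes, frozen cores |
| TIL as a percentage | 9.2.1, 13.5 | Yes, if obtained by IHC; the assay is not named |
| TIL isolation from tissue | Appendix G | No written route |
| Flow cytometry on tissue | 9.1.3 (may), 9.5 (will) | No written route |

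**The case against.** The strongest defence is that the plan omits a route without forbidding one. The storage line can be read as covering only tissue that is to be stored. The Friday rule shows that fresh processing was expected. Section 9.1.2 also has the coordinator told before each biopsy so that transfer can be arranged. Part of this stands: fresh handling was evidently intended, and a site in contact with the laboratory might do the right thing. But the storage line is the only processing instruction given for non-formalin cores, and the dry-ice note covers transport as well as shipping, without exception. A site that simply follows the text freezes the core.

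The second defence concerns consequence, and most of it stands. Section 9.1.3 makes tissue flow cytometry optional, section 13.5 describes the correlative work as largely exploratory, and section 9.4 lets assays be changed. Appendix D lists CD3, CD4 and CD8 as top-priority, optimized IHC markers, so formalin cores can supply the T-cell infiltration data that sections 1.3 and 9.1.1 ask for.

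A reader might go further and infer three things that the documents do not support:

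- **That no tissue TIL readout can be obtained for any patient.** The text lacks a route; it does not exclude one, and TIL percentages may come from IHC.
- **That biopsy cores are wasted.** Frozen cores still serve RNA and sequencing work.
- **That flow cytometry requires fresh cells.** Appendix H accepts cells that were properly cryopreserved.

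**Conclusion.** The inconsistency is real and lies in specimen handling. Section 9.1.2 cannot be followed literally and still feed Appendix G, and Appendix C does not close the gap. If sites follow the text, the flow-based tissue readouts would probably fail.

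This conclusion rests on two assumptions: that sites apply the storage line and dry-ice note as written, and that tissue frozen without cryoprotectant or held in RNAlater yields no usable live cells. The first is the natural reading. The second is general laboratory knowledge with only indirect support in the documents.

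The size is modest. The loss is limited to readouts that are exploratory and, in section 9.1.3, optional. It does not extend to IHC, mRNA, sequencing or the 3-month progression-free survival endpoint. Nor can it be said that the 16-pair TIL comparison in section 13.5 is lost, because that section does not tie it to flow cytometry. The correction is still worth making, because it is cheap and a core frozen in this way cannot be recovered for digestion.

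**What to change.** Rewrite the handling text in section 9.1.2 by medium:

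- **RNAlater cores:** frozen at -70 to -80 C and shipped on dry ice, for RNA work.
- **DMEM cores:** kept unfrozen, taken to the laboratory within a stated time limit, processed by Appendix G, and frozen only as a cell suspension in freezing media. Remove DMEM from the frozen-storage line and from the dry-ice note.
- **Where timely transport is not possible:** use RNAlater and omit tissue flow cytometry for that sample. This also supplies the missing rule for choosing the medium.
- **Appendix C:** align the OCT freezing steps and the Fresh Tissue Shipping Procedures paragraph with section 9.1.2. Editing section 9.1.2 alone would leave a conflicting instruction in force.

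The alternative is to delete TIL isolation and tissue flow cytometry from the plan, including the commitment in section 9.5.

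The cost of the first option is a wording change, prompt local transport for the DMEM core, and no tissue flow cytometry from distant sites. No additional biopsy is needed. The alternative costs only the exploratory flow readouts.
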